This project presents an innovative proposal, addressing a BCG vaccine with known efficacy against severe TB in childhood and reliable for the use of adjuvant therapy in patients with malignant bladder neoplasia.

BCG is an easily accessible vaccine, widely used by SUS in newborn children, thus facilitating its incorporation into a new preventive proposal for COVID-19. In addition, the selection of health professionals will be based on diagnostic screening and confirmatory tests of COVID-19.

It is intended to analyze the role of BCG in the prevention of infection and also in the occurrence of severe forms of COVID-19 in addition to evaluating the immune response mediated by this vaccine in voluntary health professionals.

GOALS:

In the period of 6 months, to analyze the effect of BCG as a protective factor for COVID-19 in research volunteers, aiming at greater efficiency in the prevention of subjects at high risk of infection and evolution to severe forms of the disease, as well as to evaluate the specific and non-specific immune responses to SARS-CoV-2 in vaccinated and unvaccinated volunteers who evolved with COVID-19 or not.

Primary Objectives:

1. Assess the impact of BCG vaccine administration on the cumulative incidence of SARS-CoV-2 infection
2. Assess the impact of BCG vaccine administration on the cumulative incidence of severe forms of COVID-19
3. Evaluate the bcg vaccine-mediated immune response in volunteers

Secondary Objectives:

In groups receiving BCG or placebo, infected and not infected with SARS-CoV-2:

- Epidemiological:

1. Estimate whether BCG vaccination compared to placebo prolongs the time to the first respiratory disease proven by SARS-CoV-2;
2. Estimate whether BCG vaccination compared with placebo reduces the proportion of symptoms associated with COVID-19 (fever or at least one sign/symptom of respiratory disease);
3. Estimate whether BCG vaccination compared to placebo reduces absenteeism (missing days) in volunteers who are health professionals;
4. Analyze the safety of BCG vaccination in adult volunteers;

- Laboratories:

5. Describe the inflammatory profile by dosing neutrophils, platelets, cit-H3, alpha 1 antitrypsin (α 1AT), galectin-2, ferritin, transferrin-R, glycated hemoglobin (HbA1c),

C-reactive protein (CRP), D-dummer, LDH, albumin and hemosedimentation velocity (ESR);

6. Describe the profile of inflammatory cytokines identified in the BCG and placebo groups, comparing to the protective events to SARS-CoV-2;

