In addition to face-to-face visits, participants will receive a telephone contact or a text message by phone via SMS or receive email, the *latter two with a link* for the participant to access and answer the questionnaire about signs and symptoms of COVID as well as sending a photo with the aspect of the injection site. This will occur weekly until M3, and then monthly seeking information on fever and/or respiratory symptoms and the site of vaccine application. The participant will be asked to send a photo of the vaccine application location in each of these contacts. If the participant signals any respiratory manifestation or fever, they will be instructed to seek the Worker Health Divisions of their respective work units or the private or public health services, according to their availability, for the nasoarcheal swab to perform RT-PCR for coronavirus, as well as for medical care directed to the condition. In case of adverse events to the vaccine or

placebo, patients will be evaluated in person at the study centers where they were recruited.

If any participant presents the diagnosis of OVID-19 they will be invited to attend the study for a face-to-face visit once they are asymptomatic and 14 days after the onset of symptoms. In this face-to-face visit, the participant will answer questions from a questionnaire about signs of symptoms of the disease and will be asked to present laboratory or radiological tests performed during COVID-19 infection.

Individuals who show interest in participating in the research should not have been previously vaccinated with any specific vaccine against COVID-19 or if vaccinated, only those immunized with both doses of vaccines, and the second dose should be applied within a minimum of 15 days.

Participants already included and submitted to the intervention, must wait up to 15 days after the intervention with BCG/Placebo to receive specific vaccines against COVID-19 already approved by ANVISA for use by the National Immunization Program, according to the guidelines of the Brazilian Ministry of Health.

In the case of recruited individuals who are eligible for inclusion and intervention, but who give up receiving the investigational product of the study, they should withdraw consent to participate in the ProBCG study.

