BCG vaccine:

The application of bcg vaccine as well as its storage and the materials used for application will follow the standards of the Manual of Standards and Procedures for Vaccination of the Ministry of Health (Brazil, 2014). As standardized in this Manual, the

vaccine will be applied intradermally to the lower insertion of the deltoid muscle of the right arm, except contraindications or impossibilities. Other details are described in the standard operating manual (MOP) of the study. After the intervention, participants will be under observation for 20 minutes in the study center waiting room and will be released after the period as long as they do not present adverse events.

Placebo:

A 0.1 ml of 0.9% NaCl saline solution applied intradermally in the lower insertion of the deltoid muscle of the right arm will be used as placebo, except contraindications or impossibilities. Other details are described in the standard operating manual (MOP) of the study. After the intervention, participants will be under observation for 20 minutes in the study center waiting room and will be released after the period as long as they do not present adverse events.

Blinding:

The study participants as well as the researchers, coordinators, nurses, physicians and digitizers of the study will be blind to the allocation in the experimental or control groups.

Only nursing technicians who will apply the vaccine or placebo will be aware of which group the patient will be allocated to. This professional will not follow up on the clinical follow-up or outcome of the study participant.

If the participant has access to the COVID-19 vaccine before 15 days after vaccination with the study product, the "blinding" may be performed at the participant's written request, and if the product applied was placebo, the same may be vaccinated against COVID-19 before the 15 days established by the National Immunization Program. Other details are described in the standard operating manual (MOP) of the study.

Reaction to BCG vaccine and placebo:

The BCG vaccine known to generate a local inflammatory response that lasts about 12 weeks and will be monitored throughout the study. The reactions are described below and will not be considered as adverse events:

- From the first to the second week: reddish macula lasting from 5 mm to 15 mm in diameter.
- From the third to the fourth week: pustule that forms with the softening of the center of the lesion, followed by the appearance of crust.

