The overall incidence of adverse reactions in subjects vaccinated at the target dose was 23.73%, of which 23.24% were mild and 1.94% moderate. The preliminary safety analysis of the phase III clinical study conducted with 5,051 adult (18-59 years) and elderly (over 60 years) clinical study who received the complete regimen with 2 doses of the vaccine showed that the general frequency of occurrence of requested adverse reactions (local and systemic) up to 7 days after administration of the second dose was 50.8% in the group of adults and 36.4% in the elderly group. For unsolicited adverse reactions (local and systemic) up to 7 days after the administration of the second dose, the overall frequency of occurrence was 9.2% in the adult group and 8.1% in the elderly group. The most common reaction observed after the second dose of the vaccine in both groups was pain at the site of administration, which occurred in 40.1% of adults and 27.8% of the elderly. The vast majority of adverse reactions observed were Grade 1/2 and no serious adverse reaction occurred.

- Adverse reactions observed from phase I/II clinical studies in Adults (18-59 years) and the elderly (over 60 years):
 - Very common reaction (> 1/10): Location: pain
 - Common reaction (> 1/100 and ≤ 1/10): Systemic: fatigue, fever, myalgia, diarrhoea, nausea, headache
 - Unusual reaction (> 1/1000 and ≤ 1/100): Systemic: vomiting, lower abdominal pain, bloating, dizziness, cough, loss of appetite, hypersensitivity, high blood pressure; and Site: abnormal staining at the site of administration, swelling, itching, erythema, local hypoesthesia, hardening.

Adverse reactions observed from the phase III clinical study in Adults (18-59 years) up to 7 days after administration of the second dose of the vaccine:

- Very common reaction (> 1/10): Systemic: headache, fatigue; and Location: pain
- Common reaction (> 1/100 and ≤ 1/10): Systemic: nausea, diarrhea, myalgia, chills, loss of appetite, cough, arthralgia, itching, rinorrhoea, nasal congestion; and Location: erythema, swelling, duration, itching
- Unusual reaction (> 1/1000 and ≤ 1/100): Systemic: vomiting, fever, rash, allergic reaction, oropharyngeal pain, odynophagia, sneezing, astherries, asthesis, dizziness, abdominal pain, drowsiness, malaise, flushing, pain in the extremities, upper abdominal pain, back pain, vertigo, dyspnea, edema; and Location: hematoma

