Adverse reactions observed from the phase III clinical study in the Elderly (over 60 years) up to 7 days after the administration of the second dose of the vaccine:

- Very common reaction (> 1/10): Location: pain
- Common reaction (> 1/100 and ≤ 1/10): Systemic: nausea, diarrhea, headache, fatigue, myalgia, cough, arthralgia, itching, rinorrhoea, odinofagia, nasal congestion; and Location: itching, erythema, local edema, duration
- Unusual reaction (> 1/1000 and ≤ 1/100): Systemic: vomiting, chills, decreased appetite, allergic reaction, asthena, dizziness, ecchymosis, hypothermia, discomfort in the limbs; and Location: hematoma

In addition, there are theoretical risks that vaccinated individuals could develop a more serious disease, but so far there is no report that this has happened to the virus that causes COVID-19. This vaccine was previously tested in animals and they did not present this form of infection more severe.

Adverse events related to Covishield Vaccine®:

The overall safety of the Covishield® vaccine (recombinant) is based on the interim analysis of grouped data from four clinical studies conducted in the UK, Brazil and South Africa. At the time of analysis, 23,745 \geq 18 years had been randomized and received the vaccine or control. Of these, 12,021 received at least one dose of the recombinant vaccine. Demographic characteristics were generally similar among individuals who received the vaccine and those who received control. Overall, among the individuals who received the recombinant vaccine, 90.3% were between 18 and 64 years old and 9.7% were older than 65 years or more. Most individuals were white (75.5%), 10.1% were black and 3.5% Asian; 55.8% were women and 44.2% were men. The most frequently reported adverse reactions were injection site sensitivity (> 60%); injection site pain, headache, fatigue (> 50%); myalgia, malaise (> 40%); pyrexia, chills (> 30%); and arthralgia, nausea (> 20%). Most adverse reactions were mild to moderate in intensity and usually resolved within a few days after vaccination. Compared to the first dose, adverse reactions reported after the second dose were lighter and less frequently reported.

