According to CNS Resolution No. 441 of 2011 (Art. 1) and Ordinance MS No. 2,201 of 2011 (Art. 3), any organized collection of human biological material collected for scientific research purposes, including samples intended for routine examinations in a clinical trial (e.g., blood count and renal function) are considered as constituents of a biorepository or biobank. The biological material will be used as provided for in the research protocol, with no further future analyses different from those foreseen. If there is a proposal for future use of the stored samples, approval in the CEP/CONEP system will be required and a new protocol and TCLE will be submitted so that each participant can choose whether or not to allow the use of the samples for future studies.

Statistical Analysis Plan:

The primary efficacy analysis will compare the cumulative incidence of SARS-CoV-2 infection and the cumulative incidence of severe forms of COVID-19.

These analyses will occur when the last enrolled research subject has completed 30 days and 6 months of preventive treatment and will be performed using the results of COVID-19 diagnostic tests, as well as the data available in participating hospitals and national electronic notification systems of COVID-19. A modified treatment intention analysis (MITT) and protocol (PP) will be performed. The safety and tolerability analysis will consist of all patients who have been randomized and received a dose of the vaccine or placebo. Based on serum immune response concentrations, we will calculate certain immunoinflammatory variables related to the use of BCG versus placebo among subjects infected and not infected by COVID-19 among the categories with COVID-19 vaccine (Coronavac® or Covishield®) and without covid-19 vaccine.

The intervention and control groups will be compared at the time of inclusion in the study in relation to sociodemographic, clinical, radiological and biochemical imaging variables, in order to evaluate the adequacy of the randomization process. Multivariate

analyses using logistic regression or Poisson models with robust variance will be used to evaluate the effect of BCG vaccine on primary and secondary outcomes. Associations will be expressed in the form of risk ratios and respective 95% confidence intervals. Data imputation may be required and the *random forest system* will be used. Statistical software R, version 10.0.

Sample size:

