An early safety assessment will be carried out when the first 100 participants (approximately 50 per arm) are included. Security data will be reviewed by a CMDS member or someone designated by a CMDS member. In addition, the Committee will review the progress of the study after the inclusion of every 100 additional participants through real-time meetings by videoconference.

CMDS activity plan:

Time of study	Activity	Form
---------------	----------	------

Before the start of the study	Protocol and MOP review	Real-time video conferencing scheduling
During the study	Early safety assessment after inclusion of the first 100 participants	Real-time video conferencing scheduling
	Evaluation of study progression per 100 participants included	Real-time video conferencing scheduling
	Adverse event analysis	Real-time video conferencing scheduling every 2 weeks
	Analysis of serious adverse events	Extraordinary meeting via real-time videoconferencing
	Intermediate analysis after the inclusion of 500 participants	Real-time video conferencing scheduling
At the close of the study	Evaluation of the conduct of the study and its results	Real-time video conferencing scheduling

Plan for monitoring and analysis of adverse events:

The definition for an adverse event described in the Manual for Notification of Adverse Events and Safety Monitoring in Clinical Trials (Anvisa, 2016) will be used as a definition for an adverse event: "any adverse medical occurrence in a patient or clinical trial participant to whom a pharmaceutical product has been administered and who does not necessarily have a causal relationship to treatment. As a result, an AE can be any unfavorable and unintentional sign, symptom, or disease (including results outside the reference range), associated with the use of a product under investigation, whether related to it or not. A serious AE shall be considered to have one resulting in any adverse experience with medicinal products, biological products or devices occurring at any dose and resulting in any of the following outcomes: a) death; b) threat to life; (c) persistent or significant disability/disability; d) requires hospitalization or prolongs hospitalization; e) congenital anomaly or birth defect; f) any suspected transmission of infectious agent by means of a drug or; g) clinically significant event."

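### The safety analysis has no rule for reactions to COVID-19 vaccines given on study, which can dilute, and before day 15 bias, the BCG-versus-placebo comparison of non-serious adverse events

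*Combined protocol and SAP*

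**What the plan says.** Safety is item 4 of the Secondary Objectives: "Analyze the safety of BCG vaccination in adult volunteers". The Statistical Analysis Plan gives it one sentence, which names the analysis population: "The safety and tolerability analysis will consist of all patients who have been randomized and received a dose of the vaccine or placebo". It sets no adverse-event endpoint, no onset window and no rule for COVID-19 vaccination. For primary and secondary outcomes generally, "Associations will be expressed in the form of risk ratios and respective 95% confidence intervals".

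Both adverse-event sections define an event as any unfavourable sign, symptom or disease "associated with the use of a product under investigation, whether related to it or not". The section on reactions to BCG and placebo exempts the expected local BCG lesion, from macula to scar over about 12 weeks.

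COVID-19 vaccination during follow-up is allowed. Under Study visits, participants "must wait up to 15 days after the intervention with BCG/Placebo to receive specific vaccines against COVID-19". Under Blinding, a participant offered the vaccine sooner may ask in writing to be unblinded, and "if the product applied was placebo, the same may be vaccinated against COVID-19 before the 15 days established by the National Immunization Program". No such route is given for BCG recipients.

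The protocol supplies its own reaction rates. For Coronavac they are 23.73% overall in phase I/II; in phase III the frequency of solicited reactions "up to 7 days after administration of the second dose was 50.8% in the group of adults", with 36.4% in the elderly. For Covishield, injection-site sensitivity exceeds 60% and pyrexia exceeds 30%.

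Rules for COVID-19 vaccination exist only for diagnosing infection by serology, for the adjuvant-effect objectives in the vaccinated subgroup, and for the immune variables. None concerns adverse events.

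**The concern.** A COVID-19 vaccine given on study can produce fever, fatigue, headache and arm pain. These overlap with the non-specific events that an injected vaccine such as BCG might cause. Because the expected BCG lesion is not an adverse event, a comparison of non-serious events rests largely on such non-specific events.

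There are two separate effects. After day 15 either arm may be vaccinated, so the reactions are a common background that pulls the ratio towards 1 and costs power. Before day 15 the plan permits vaccination only in placebo recipients who have been unblinded, so reactions add events to one arm and shift the comparison in favour of BCG. Either way, a real excess of non-specific events after BCG could be reported as no difference. The interpretation matters because the protocol adopts no formal stopping rule for safety.

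**Working it through.** **The plan's own figures.** No safety figure is stated. The nearest stated numbers are the expected infections under Outcomes, item 3, which use 80% COVID-19 vaccination in each arm of 376:
- BCG only: 376 × 0.20 × 0.20 = 15.0
- neither vaccine: 376 × 0.20 × 0.30 = 22.6
- COVID-19 vaccine only: 376 × 0.80 × 0.15 = 45.1
- both: 45.1 × 0.85 = 38.4

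These reproduce the stated 15, 23, 45 and 38. The 80% therefore means 376 × 0.80 = 301 vaccinated people per arm. It is total coverage: Inclusion criterion 4 admits people fully vaccinated before entry, and the plan does not split the two.

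**Inputs for the safety comparison.**
- From the documents: 376 per arm and reaction rates r of 23.73%, 36.4%, 50.8% and 60%. The last is the Covishield injection-site figure, stated as above 60%.
- Assumed, because the documents give none: true risk of a non-exempt adverse event of 10% (BCG) versus 5% (placebo); share vaccinated on study v of 20% to 80%; share of placebo recipients vaccinated before day 15 q of 1% to 10%.
- Reactions are taken as independent of other events and as always recorded.

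**After day 15 (both arms).** Observed risk = 1 − (1 − p)(1 − v × r). Example with v = 0.20 and r = 0.2373: v × r = 0.0475; placebo 1 − 0.95 × 0.9525 = 0.095; BCG 1 − 0.90 × 0.9525 = 0.143; ratio 1.50. Power is two-sided at 5% for two proportions. Without COVID-19 vaccination it is 74%.

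| Reaction rate r | v = 20%: ratio (power) | v = 80%: ratio (power) |
|---|---|---|
| 23.73% | 1.50 (52%) | 1.18 (25%) |
| 36.4% | 1.39 (44%) | 1.11 (17%) |
| 50.8% | 1.31 (38%) | 1.07 (13%) |
| 60% | 1.27 (34%) | 1.05 (11%) |

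Other assumed risks behave the same way. For 20% placebo versus 30% BCG (ratio 1.50, power 89%) at r = 50.8%, the ratio appears as 1.32 (power 75%) at v = 20% and 1.11 (power 37%) at v = 80%.

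**Before day 15 (placebo only).** The BCG risk stays at 10%. Placebo risk = 1 − 0.95 × (1 − q × r).

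| q (people out of 376) | ratio at r = 23.73% | ratio at r = 50.8% | ratio at r = 60% |
|---|---|---|---|
| 1% (about 4) | 1.91 | 1.82 | 1.80 |
| 5% (about 19) | 1.63 | 1.35 | 1.27 |
| 10% (about 38) | 1.38 | 1.02 | 0.93 |

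The 5-point excess is cancelled when q × r = 1 − 0.90/0.95 = 0.0526. That is q = 8.8% at r = 60%, 10.4% at r = 50.8% and 22% at r = 23.73%.

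**The case against.** Several points on the other side stand.

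- A reader might infer that the plan compares all adverse events over six months. The Statistical Analysis Plan does not say so. That is the default reading of a population-only sentence, an event definition regardless of relatedness, and six months of follow-up. The defect is an unspecified analysis. The adverse-event form in the operations manual is not available here, so attribution at event level cannot be ruled in or out.
- Reaction rates are not recording rates. The 50.8% covers solicited reactions and is largely injection-site pain (40.1%). The trial's remote contacts ask about fever, respiratory symptoms and the study injection site, not about pain from another vaccine. Fever after Coronavac is listed as uncommon in phase III adults, although Covishield pyrexia exceeds 30%.
- A reader might take 80% as the share vaccinated on study. It is total coverage, so it is at most an upper bound.
- Early unblinding needs a written request, and unvaccinated entrants agree beforehand to wait 15 days. Uptake may be low; at 1% the ratio is still 1.8 to 1.9.
- A reader might infer that BCG harm in general would be hidden. The lesions listed as BCG-related can be told apart, the interim safety outcome is serious events, and the cited Coronavac phase III data report no serious reaction.

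The separate objectives for COVID-19-vaccinated participants do not close the gap. They seek an adjuvant effect, and within that subgroup vaccine reactions would remain in the same count. The committee's two-weekly event review is a safeguard for participants, but it does not define the final comparison.

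**Conclusion.** The concern holds for non-serious, non-specific adverse events. The safety analysis does not say how events after on-study COVID-19 vaccination are handled, and the unblinding rule makes vaccination before day 15 a placebo-only possibility. On the default reading the first effect dilutes the contrast and the second favours BCG.

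The size cannot be fixed from the documents. Under an assumed true ratio of 2.0, the observed ratio lies between 1.50 and 1.05 from dilution alone. From early placebo-only vaccination alone it lies between about 1.9 and 0.9. Both ranges rest on assumed event risks, on-study coverage and early-unblinding uptake. They should be read as upper-end effects, because not every reaction would be recorded and 80% includes vaccination before inclusion. The documents do not support extending the conclusion to serious events or BCG-specific lesions.

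**What to change.** In the Statistical Analysis Plan, after the sentence defining the safety population:

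1. Keep the comparison of all adverse events over the full follow-up, and state that period.
2. Add a pre-specified BCG-versus-placebo comparison, as event rates per person-time, that leaves out events with onset within 7 days after any COVID-19 vaccine dose and the matching person-time. Seven days is the window of the protocol's Coronavac phase III reaction figures.
3. Tabulate the left-out events separately by arm, and by before or after day 15.
4. Count serious adverse events and the listed BCG-specific lesions over the whole follow-up.

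Do not censor at the first COVID-19 dose. Before day 15 such censoring would occur only in unblinded placebo recipients. Later it could end observation before the pustule and ulcer stages that the protocol places in weeks 3 to 5, and before abscess or lymphadenopathy could be seen.

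The cost is SAP wording, one extra table and slightly less person-time: for two doses on study, 14 of about 180 days, or 8%. Before day 15 that small gap would fall on placebo recipients only, which is one reason to keep the all-events comparison beside it. The COVID-19 vaccination dates are already needed for the adjuvant-effect objectives. No clinical rule changes.
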